twice, in single scanning sessions separated by two weeks, while the remaining 20 NL subjects will be scanned four times back to back in one session, then again back to back in a second session 2 weeks later. In addition to using the preparatory phase of the study to determine the optimal scanning sequences to be used, considerable effort will be devoted to developing and testing QA and QC for the acquisition and transmission of MRI and PET images. Based on data derived from the preparatory phase, final sequences will be chosen for this study.

D. ADNI STUDY

D1. SYNOPSIS-ADNI STUDY

We propose a multi-center biomarker trial to identify biomarkers of disease progression that are most promising as surrogate endpoints in phase 2 and 3 clinical trials for the prevention and treatment of AD. We will enroll a total of 800 subjects with 400 subjects with MCI, 200 with early AD and 200 normal controls. Subjects with MCI and controls will be followed for 3 years, those with AD for 2 years. At 6 month intervals, all subjects will be seen in person or contacted by telephone. Subjects will undergo clinical and neuropsychological evaluations each time scanning is performed. All subjects will undergo repeated 1.5T MRI scanning (MCI-N=6 scans/subject, Controls-N=5 scans/subject, AD-N=4 scans/subject), 25% will undergo repeated 3T MRI scanning, and 50% will undergo repeated PET scanning with the same frequency of scanning used for the 1.5T MRI imaging. Blood and urine biomarkers will be collected at each interval when imaging data is collected from all participants. Immortalized cell lines will be established from all subjects at baseline. All subjects will be approached for LP so that a minimum of 20% and as many as 50% of each group will undergo lumbar puncture at baseline and at year 1 for analysis and storage of CSF.

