 - Qualititave: imaging begins at 30 min post injection, and the scan is acquired as six 5-min frames
 - Quantitative: imaging begins at injection, and the scan is acquired as 27 frames over 60 min. Five venous blood samples will be drawn and counted for both plasma glucose and [¹⁸F]FDG throughout the 60 min study.
- Subjects will also received a transmission scan. This can either be a short CT scan for PET/CT systems, or a rotating positron source for PET only scanners.
- All PET data for the subject will be de-identified and sent to the data repository maintained at LONI at UCLA.
- Subjects will return for repeat PET scans at the intervals outlined in the "Schedule of Events" specific to the subject's classification.
- See procedures manual for further details

D.5.t. ENDPOINT DETERMINATION

The conversion from normal to MCI or AD, and conversion from MCI to AD is of considerable interest. We estimate that the most frequent conversion will be from MCI to AD which will occur at approximately 10-15% per annum. Thus, allowing for a 10% dropout rate, using an estimated conversion rate of 12%, we estimate that there will be 119 conversions from MCI to AD during the course of the trial. All conversions from one state to another will initially be made by clinicians at each site then reviewed by a central review committee. Diagnostic classification at each site will be a multiple step procedure. First, a study clinician (nurse or physician) will assess the subject by performing a clinical interview. The clinical interview should be performed at each visit without referring to other neuropsychological testing, adverse effects, and laboratory data. After interviewing the subject and study partner, the clinician will complete the Clinical Dementia Rating.

Second, a psychometrist will perform the Alzheimer's Disease Assessment Scale–Cognitive (ADAS-COG), the neuropsychological battery, and the Mini-Mental State Examination (MMSE). A nurse or psychometrist will administer the FAQ, GDS and NPI-Q.

A nurse or physician will collect the intervening adverse events, concurrent medications, and perform vital signs. Biomarker samples will be acquired, when relevant.

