D.11.c. REPORTING SERIOUS ADVERSE EVENTS

Any such experience due to any cause, which occurs during the course of the investigation or within 30 days of the last study visit, must be reported to the Project Director within 24 hours after learning of the event. This is in turn will trigger a report to be distributed to all participating sites, IRBs, and the NIA.

D.12. STATISTICAL CONSIDERATIONS

D.12.a STUDY ASSIGNMENT

Depending on the subject's consent the subject will be enrolled in the arm with the lowest percentage of target enrollment. To ensure the minimum number of CSF samples are collected, sites will not be allowed to enroll their third participant in each arm (NL, MCI, AD) unless two of the first 3 have agreed to lumbar puncture. Extensive reporting and monitoring of enrollment progress will feed back to the ADNI-CC to ensure recruitment goals are met.

D.12.b STATISTICAL POWER

The sample sizes chosen (NL=200, MCI=400, AD=200) are designed to meet the needs of the hypotheses being tested for the proposed imaging and biochemical biomarkers.

Between-diagnostic group analyses: These analyses will mainly be confirmatory analyses to verify that the imaging measures and biomarkers behave as expected, differing across diagnostic categories in level and rate of change. An effect size in these analyses describes how the variance of the group means compares to the common variance of the observations within each group. With the chosen sample sizes, we will have 80% power to detect an effect size of 0.01, at level alpha=0.05 (0.02, at level alpha=0.01) between rates of change in the 3 clinical groups for MRI and biomarkers, 0.03 (0.04) for PET, and 0.05 (0.08) for MRI at 3 Tesla.

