Within diagnostic group analyses: The primary focus of this proposal is to provide imaging and biomarker information that will help in planning future clinical trials, which are likely to be conducted within a particular diagnostic category. Therefore, we present power separately for MCI and the smaller groups of AD and normals. These analyses will have two primary goals: 1) to assess the strength of association between imaging summaries and clinical measures, and 2) to better understand the between- and within-subject variation to correlate longitudinal change in imaging with longitudinal change in clinical measures. We will have 80% power to detect an association attributed to the imaging or biomarker measures accounting for 2.1% at level alpha=0.05, (3.2%, at level alpha=0.01) of the variability in the clinical measures or imaging measures, 4.2% (6.2%) for PET, and 8.2% (11.9%) for MRI at 3 Tesla within the MCI patients and 4.2% (6.2%) for MRI, 8.2% (11.9%) for PET, and 15.4% (21.9%) for MRI at 3 Tesla within the normal or AD subjects.

We will have 80% power to detect a correlation of 0.15 at level, alpha=0.05 (0.18, at level, alpha=0.01) between MRI or biomarker and the clinical outcome, 0.21 (0.25) for PET, and 0.29 (0.35) for 3-Tesla MRI in the MCI subjects and 0.21 (0.25) for MRI, 0.29 (0.35) for PET, and 0.39 (0.47) for 3-Tesla MRI in the AD or normal subjects. Under a multivariate normal assumption, we would, for example, be able to construct 95% confidence intervals around an estimated correlation of 0.5 of the following: (0.42, 0.57) for MRI, (0.38, 0.60) for PET, and (0.33,0.64) for 3-Tesla MRI within the MCI subjects and (0.38,0.60) for MRI, (0.33,0.64) for PET, and (0.24,0.69) for 3-Tesla MRI within the normal or AD subjects.

D.12.c. STATISTICAL ANALYSES FOR HYPOTHESES

Numerous hypotheses based on the clinical and biomarker data will be evaluated. Analyses by gender and minority status will also be conducted as required by NIH policy. Five examples will be discussed here:

1. Rates of conversion from MCI to AD will average 10-15%/year. Annual conversion rates will be assessed using Kaplan-Meier product limit estimators at the conclusion of the investigation. To estimate the anticipated precision of the incidence estimates, a sensitivity analysis of the 95% confidence interval for conversion rate from MCI to AD was conducted using life table probabilities.

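### D.12.b rounds the detectable between-group effect for MRI and biomarkers down to 0.01, where power is 67% to 72% and not the stated 80%

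*Protocol*

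**What the plan says.** Protocol D.12.b opens with the enrolment targets: "The sample sizes chosen (NL=200, MCI=400, AD=200"). For the between-diagnostic-group analyses it defines its measure: "An effect size in these analyses describes how the variance of the group means compares to the common variance of the observations within each group". It then attributes the power figures to the chosen sample sizes and says that "we will have 80% power to detect an effect size of 0.01, at level alpha=0.05 (0.02, at level alpha=0.01") for rates of change in MRI and biomarkers, followed by "0.03 (0.04) for PET, and 0.05 (0.08) for MRI at 3 Tesla". All six effects carry two decimals. The section does not say that they are rounded, and it gives neither a dropout rate nor an analysed N.

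The subset shares are in D1: "25% will undergo repeated 3T MRI scanning, and 50% will undergo repeated PET scanning". A dropout allowance appears in D.5.t, where the expected number of conversions is worked out "allowing for a 10% dropout rate".

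For the within-group analyses, D.12.b prints detectable shares of variance to a tenth of a percent, and detectable correlations that include "0.39 (0.47) for 3-Tesla MRI in the AD or normal subjects".

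**The concern.** The effect defined in D.12.b is Cohen's f². For a three-group F test, f², N and alpha determine the power, so the printed pairing of 80% with 0.01 can be checked directly. With all 800 subjects it misses by more than 8 points, and any attrition makes it worse.

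D.12.b says that the study's main purpose is to supply information for planning future trials. A reader who takes 0.01 at face value would credit the design with more sensitivity than it has. No sample size, test or decision in this protocol depends on the figure, so what is at stake is the accuracy of a stated power claim, not the validity of the study.

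**Working it through.** **Inputs.** Groups of 200, 400 and 200, total 800 (D.12.b). PET in 50%, so 400; 3T in 25%, so 200 (D1). Dropout 10% (D.5.t), giving 0.9 × 800 = 720, 0.9 × 400 = 360 and 0.9 × 200 = 180. Effect size f² as defined in D.12.b, with the variance of the group means weighted by group size (my assumption; unweighted readings are checked below).

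**Formula.** One-way comparison of k = 3 groups. Power = 1 − F′(c; 2, N−3, λ), where F′ is the noncentral F distribution function, c is the central F quantile at 1 − alpha on 2 and N−3 degrees of freedom, and λ = N × f².

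**Reproducing the protocol's figures.** Solving for the f² that gives 80% power, alpha 0.05 (0.01):

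| Measure | Printed | Full enrolment | 90% of enrolment |
|---|---|---|---|
| MRI, biomarkers | 0.01 (0.02) | N=800: 0.0121 (0.0175) | N=720: 0.0134 (0.0194) |
| PET | 0.03 (0.04) | N=400: 0.0243 (0.0351) | N=360: 0.0270 (0.0391) |
| 3T MRI | 0.05 (0.08) | N=200: 0.0489 (0.0711) | N=180: 0.0544 (0.0792) |

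The last column rounds to all six printed values. The full-enrolment column does not: PET at alpha 0.05 would round to 0.02, and 3T at alpha 0.01 to 0.07.

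The within-group figures point to the same N. With one predictor, the variance share detectable with 80% power at alpha 0.05 is 2.14%, 4.22%, 8.19% and 15.44% at n = 360, 180, 90 and 45, against the printed 2.1%, 4.2%, 8.2% and 15.4%. For a correlation of 0.5, the Fisher Z interval at n=45 is (0.242, 0.692), which matches the printed (0.24, 0.69); n=50 gives (0.257, 0.683).

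**Power at the printed effects,** alpha 0.05 (0.01):

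| Measure | Full enrolment | 90% of enrolment |
|---|---|---|
| MRI, biomarkers at 0.01 (0.02) | 71.6% (86.4%) | 66.7% (81.5%) |
| PET at 0.03 (0.04) | 88.1% (86.2%) | 84.3% (81.2%) |
| 3T at 0.05 (0.08) | 80.9% (85.6%) | 76.3% (80.5%) |

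For the MRI value, λ = 800 × 0.01 = 8.0 or 720 × 0.01 = 7.2. Reaching 80% at exactly 0.01 takes 967 subjects. The overstatement is 80 − 71.6 = 8.4 points or 80 − 66.7 = 13.3 points. Against 0.0134, the printed effect is low by (0.0134 − 0.01)/0.0134 = 25%.

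**Other readings of an exact 0.01, N=800.** Read as R², power is 72.0%. Read as f, it is about 6%. With an unweighted variance of the means, it is 41% to 77% over the mean patterns tried. None reaches 80%.

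**Correlations at n=45.** The printed 0.39 (0.47) are the square roots of the printed variance shares: √0.154 = 0.392 and √0.219 = 0.468. At those shares the fixed-predictor F test has 79.9% power at both alpha levels. By Fisher Z at n=45, the power at 0.39 (0.47) is 76.1% (76.7%), and the correlations detectable with 80% power are 0.41 (0.48).

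**The case against.** The strongest reply is that nothing was miscalculated. The six effects are printed to two decimals, and 0.0134 (or 0.0121) is 0.01 at that precision. Four of the six values (0.02, 0.03, 0.04 and 0.08) were rounded up and so understate the design's sensitivity. The protocol calls these comparisons mainly confirmatory and puts its primary focus on the within-group analyses, whose variance shares reproduce. The one concrete three-group difference in the document, the plasma isoprostane means of 0.66, 0.44 and 0.19 with SD 0.16 in D.12.c, is far larger than either 0.010 or 0.013.

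All of this stands as to cause and consequence. It does not rescue the sentence as printed. Rounding a minimum detectable effect down always overstates power, and with one significant digit left the loss is material. Read as a rounded number, 0.01 covers 0.005 to 0.015, over which power at N=800 runs from 41% to 88%. The same section prints its variance shares to a tenth of a percent, so finer precision was in use there.

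A reader might go further and infer that the power calculation is wrong, or that the detectable effects are generally set too low. The documents do not support either. The full set reproduces at 90% of enrolment, and at full enrolment the other five between-group values give 81% to 88% power. The 3T value of 0.05 falls short only at N=180. The n=45 correlations fall short only if Fisher Z replaces the fixed-predictor test; at n=50 Fisher Z gives 81% (82%). D.12.c assumes 10% dropout per year for the conversion estimates. Carried over three years, that would leave about 583, 292 and 146 subjects and put all six between-group values below 80%, but those sample sizes do not reproduce the printed figures.

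**Conclusion.** The point holds as a defect of precision in one stated power figure. At alpha 0.05 the effect of 0.01 for MRI and biomarkers carries 71.6% power with all 800 subjects and 66.7% with 720; the value that carries 80% is 0.0121 or 0.0134 respectively. The 3T value of 0.05 is a lesser instance of the same rounding, at 76.3% with N=180 and 80.9% with N=200.

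This rests on reading the effect size as f² with means weighted by group size, and on the omnibus F test. The 720/360/180 basis is inferred from the agreement of the printed figures, because D.12.b does not state it. The shortfall at 0.01 does not depend on that inference.

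**What to change.** In D.12.b, state the planning N (720 for MRI and biomarkers, 360 for PET, 180 for 3T, after 10% dropout) in place of the bare reference to the chosen sample sizes. Print the between-group effects to three decimals: MRI and biomarkers 0.013 (0.019), PET 0.027 (0.039), 3T 0.054 (0.079). At the planning N these give between 78.6% and 80.0% power; if a strict 80% is wanted, give 0.0134 for the first value or round every detectable effect up.

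Optionally, add that 0.39 (0.47) at n=45 derives from the fixed-predictor variance share and would be 0.41 (0.48) by Fisher Z.

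The cost is a text correction. Enrolment, tests and schedule are unchanged. The MRI and 3T figures at alpha 0.05 become slightly less favourable, and the other four slightly more so.

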The methods described below will be utilized for the collection, aliquoting, storage, archiving, tracking of all samples collected from subjects in this grant. In addition to the screening labs described earlier in this application, and the AD biomarkers summarized above, lymphoblastoid cell lines will be established and the APOE genotype will be determined. To accomplish this, we will: (A) Generate EBV immortalized cells of all selected subjects using blood cells sent in 2 ACD-A 8.5 mL tubes by overnight delivery at room temperature to arrive at the National Cell Repository for Alzheimer's Disease (NCRAD) within 24 hours of sample harvesting. Upon arrival at NCRAD the blood sample is placed in a centrifuge and spin to separate the sample into three main layers: the red bloodcell layer, the plasma layer, and the buffy coat, which contains the white-blood cells. The white-blood cells are needed to establish cell lines and obtain DNA. To establish cell lines, the white-blood cells are placed in a flask along with a solution that allows permanent cell growth. The cells are incubated at 37°C (body temperature) ranging from three weeks to three months. The cell-containing solution is then divided and transferred into two larger flasks for further cell growth. It takes approximately one week for the cells to divide to the desired number. The cells are then placed in a vial along with a preservative. Each vial holds approximately 1 milliliter of solution containing 1×10^7 (10,000,000) cells. The cells are gradually cooled to freezing temperatures. The slow freeze prevents damage to the cell line. The frozen cells are bar code labeled and stored in a tank filled with liquid nitrogen at -316°F. Cells can be preserved this way indefinitely and thawed at any time for additional propagation. (B) Genotype all selected subjects for APOE allele status using DNA extracted from peripheral blood cells from all selected subjects that are collected in 1 EDTA plastic tube (10 mL) sent by express mail to the UPENN AD Biofluid Bank Laboratory by overnight delivery at room temperature as described (5). (C) Perform analysis of selected analytes: isoprostanes (blood, CSF, urine), homocysteine (blood and CSF), sulfatides (CSF), Aß (CSF), and tau (CSF).

D.5.r.i. BIOLOGICAL FLUIDS TO BE COLLECTED

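### D.12.b gives all biomarkers the full-cohort power figures, but tau, Aβ and sulfatides are assayed only in CSF from 20–50% of each group, so the stated 80% does not hold for them

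*Protocol*

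**What the plan says.** Protocol D.12.b opens with the claim "The sample sizes chosen (NL=200, MCI=400, AD=200) are designed to meet the needs of the hypotheses being tested" for the imaging and biochemical biomarkers. It then groups biomarkers with 1.5T MRI in three places:

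- Between diagnostic groups, an effect size of 0.01 at alpha 0.05 (0.02 at alpha 0.01) "between rates of change in the 3 clinical groups for MRI and biomarkers, 0.03 (0.04) for PET", with a further pair for 3T MRI.
- Within MCI, "80% power to detect an association attributed to the imaging or biomarker measures accounting for 2.1% at level alpha=0.05".
- Within MCI, "80% power to detect a correlation of 0.15 at level, alpha=0.05 (0.18, at level, alpha=0.01) between MRI or biomarker and the clinical outcome".

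PET (50% of subjects) and 3T MRI (25%) each receive their own, larger detectable effects. CSF receives none.

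Section D.5.r names the analytes and the fluids in which they are assayed. Isoprostanes are measured in blood, CSF and urine; the list continues "homocysteine (blood and CSF), sulfatides (CSF" only, and Aβ and tau are likewise CSF only. Section D.1 says that blood and urine come from all participants, whereas "a minimum of 20% and as many as 50% of each group will undergo lumbar puncture at baseline" and at year 1. The inclusion table in D.4.c marks CSF as optional.

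**The concern.** Three of the five named analytes can exist only for subjects who have a lumbar puncture. D.12.b recognises that a measure taken in a subset detects only larger effects, and adjusts for this with PET and 3T MRI, but it leaves CSF under a general biomarker label carrying the full-cohort figure.

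This matters because B.2 and D.1 present more definitive longitudinal data on CSF tau and Aβ as the reason for the added lumbar punctures, and D.12.b says that the primary focus is information for planning later trials. Someone who takes 80% power at r = 0.15 as applying to CSF tau could give a null result far more weight than the subset can support.

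**Working it through.** **Inputs.** Group sizes are NL 200, MCI 400 and AD 200 (D.12.b). LP uptake is 20% to 50% of each group (D.1). D.12.b states no loss rate; D.5.t uses "allowing for a 10% dropout rate" for the conversion count, and 10% is adopted here because it reproduces D.12.b. Sidedness is not stated; two-sided is assumed.

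**Formulas.**
- Correlation (Fisher z): power = Φ(atanh(r)·√(n−3) − 1.96) at alpha 0.05.
- R²: noncentral F with 1 and n−2 df, λ = n·R²/(1−R²).
- Three groups: noncentral F with 2 and N−3 df, λ = N·f², where f² is the variance of the group means over the within-group variance, the definition D.12.b gives.

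**Step 1: reproduce the plan.** In MCI, 400 × 0.9 = 360. Then atanh(0.15)·√357 = 2.856, and Φ(2.856 − 1.960) = 81.5%. At alpha 0.01, r = 0.18 gives 80.6%. Detectable R² at n = 360 is 2.14% (3.17% at alpha 0.01), matching the stated 2.1% (3.2%). At n = 400 the power for r = 0.15 would be 85.4% and detectable R² 1.93%, which does not match. The other rows follow at n = 180, 90 and 45: 4.2%, 8.2% and 15.4%. The biomarker figure in MCI is therefore the full-cohort row.

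Between groups, N = 800 × 0.9 = 720 gives 80% power at f² = 0.0134, printed as 0.01. At alpha 0.01 it gives 0.0194, printed as 0.02.

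**Step 2: put in the CSF numbers.** In MCI, 400 × 0.20 × 0.9 = 72 and 400 × 0.50 × 0.9 = 180. Overall, 800 × 0.20 × 0.9 = 144 and 800 × 0.50 × 0.9 = 360.

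| Power for a CSF-only analyte, alpha 0.05 | 20% LP | 50% LP |
|---|---|---|
| MCI, r = 0.15, after 10% loss | 24% (n = 72) | 52% (n = 180) |
| MCI, r = 0.15, no loss | 26% (n = 80) | 56% (n = 200) |
| MCI, R² = 2.1%, after 10% loss | 23% | 50% |
| Between groups, f² = 0.0134, after 10% loss | 21% (21.5%; N = 144) | 49% (48.5%; N = 360) |

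For example, at n = 72, atanh(0.15)·√69 = 1.255 and Φ(1.255 − 1.960) = 24%.

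**Step 3: effects detectable with 80% power, alpha 0.05, after 10% loss.**

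| | Full cohort (as printed) | CSF, 20% LP | CSF, 50% LP |
|---|---|---|---|
| MCI, R² | 2.1% | 10.1% | 4.2% |
| MCI, r (= √R²) | 0.15 | 0.32 | 0.21 |
| Between groups, f² | 0.01 (0.0134 unrounded) | 0.068 | 0.027 |

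Fisher z gives 0.33 instead of 0.32 in the 20% column; the difference is one of method only. At the 50% goal, CSF in MCI coincides with the plan's PET row (4.2%). At the 20% floor it is worse than the plan's 3T row (8.2%).

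**The case against.** The best defence is that the figure is right for the biomarkers the statistical section actually discusses. The only biomarker hypothesis in A.2, and the only one worked through in D.12.c, concerns plasma isoprostanes, available in the whole cohort; blood homocysteine is too. B.2 says that funding limits put the emphasis on sample collection and banking, and A.2 puts data collection ahead of analysis. This stands: the calculation itself is correct, and the fault is a label that is too broad. A reader might infer that the whole biomarker programme is underpowered; the documents do not support that.

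Second, D.12.a stops a site from enrolling a third subject in an arm unless two of the first three accept LP. If about 50 sites each enrol at least three per arm, that is about 100 consenting subjects per arm: 50% of NL and AD, but 25% of MCI. Consent is not completion, and the number per site is an assumption. The rule makes the 20% floor look pessimistic, especially for NL and AD. It does not rescue the MCI figure: at n = 100, power for r = 0.15 is 32%.

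Third, a reader might compute between-group power at exactly 0.01 and report 17% (N = 144) to 38% (N = 360). That overstates the loss. The 0.01 is rounded, and even N = 720 has only 67% power at that value, so the comparison belongs at 0.0134.

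Fourth, a reader might infer that the NL and AD biomarker figures are also wrong. Those clauses of D.12.b name only MRI, PET and 3T MRI, so there is no NL or AD biomarker figure to correct.

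**Conclusion.** The point holds for tau, Aβ and sulfatides, and for CSF assays of the other analytes. It does not hold for blood or urine biomarkers. No LP rate within the plan's own range gives the stated 80%: in MCI at r = 0.15, power runs from about a quarter at the floor to just over a half at the goal.

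The exact values rest on two assumptions, the 10% loss and two-sided testing. Removing the loss adds only 2 to 4 points in MCI. Where in the range the study falls depends on LP uptake.

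Severity is should-fix. D.12.b calls the between-group analyses mainly confirmatory, and the document rests no sample size or stopping decision on CSF power. The statement is nevertheless wrong as written for the analytes that motivate the LP extension.

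**What to change.** In D.12.b, wherever biomarkers share a figure with 1.5T MRI (the between-group effect size and the two MCI statements), limit the term to blood and urine analytes. Add a CSF row giving the effects detectable with 80% power at alpha 0.05 for the 20% floor and the 50% goal:

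- MCI: R² 10.1% and 4.2% (r about 0.32 and 0.21).
- Between groups: effect size 0.068 and 0.027.

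State the loss rate and sidedness on which all rows rest. CSF values for NL or AD (R² 18.8% at n = 36 and 8.2% at n = 90; r about 0.43 and 0.29) may be added as new information.

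The cost is a few words and one added row. No subjects or procedures are added, but the stated capability for CSF becomes less favourable.
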